**Table 2 Optional Dose Increase or Mandatory Reduction Levels for Subjects initiating treatment at 15 mg daily**

+2 Dose Level	25 mg BID daily for 28 days per cycle
+1 Dose Level	20 mg BID daily for 28 days per cycle
Starting Dose	15 mg BID daily for 28 days per cycle
-1 Dose Level	10 mg BID daily for 28 days per cycle
-2 Dose Level	5 mg BID daily for 28 days per cycle

**Table 3 Optional Dose Increase or Mandatory Reduction Levels for Subjects initiating treatment at 10 mg daily**

+3 Dose Level	25 mg BID daily for 28 days per cycle
+2 Dose Level	20 mg BID daily for 28 days per cycle
+1 Dose Level	15 mg BID daily for 28 days per cycle
Starting Dose	10 mg BID daily for 28 days per cycle
-1 Dose Level	5 mg BID daily for 28 days per cycle

In summary, it is the intention to identify the optimal dose for each individual subject over the first several weeks of therapy as follows:

- Starting dose determined by baseline platelet count level.
- Optional dose increase after every 2 cycles if an objective response (PR or CR) was not achieved and no significant thrombocytopenia or neutropenia was observed.
- Frequent monitoring of hematology parameters, with mandatory dose decreases for toxicities.

### **9.3 Concomitant Medications / Measures**

All concomitant medications and treatments must be recorded in the eCRF. Any prior medication received up to 30 days prior to randomization will be recorded in the eCRF. Concomitant treatments that are required to manage a subject's medical condition during the trial will also be recorded in the eCRF.

## **9.4        Restricted and / or Prohibited Medications and Therapies**

### **9.4.1        Restricted Therapies**

The following medications have restrictions on use or doses or require changes to the way in which study drug is administered during the study:

- Systemic corticosteroid doses should not be given except when necessary for non-lymphoma related conditions and must not exceed a daily dose of prednisolone 10mg/day;
- Aspirin in doses exceeding 150 mg per day is not permitted. Low dose aspirin ( $\leq$  150 mg/day) and non steroidal anti-inflammatory agents (acetaminophen, ibuprofen) may be used;
- Potent systemic inhibitors of CYP3A4 metabolizing enzymes (ketoconazole, clarithromycin, itraconazole, nefazodone and telithromycin should not be given. When concomitant administration of a potent systemic inhibitor of CYP3A4 is required for subject management, and no alternative therapies are available, the sponsor must be contacted for discussion on a case by case basis. Subjects may not receive ruxolitinib concurrently with potent systemic inhibitors of CYP3A4 without prior approval by the sponsor, and in most cases ruxolitinib dose adjustments will be necessary.
- When concomitant administration of an anticoagulant/antiplatelet medication is required for subject management, the platelet count history, and any observations of thrombocytopenia during the study while on ruxolitinib should be considered.
- During the study, use of CYP3A4 inducers is discouraged, and investigators should consider alternative therapies wherever possible. No dose adjustment will be used when moderate CYP3A4 inducers are co-administered with study drug. Any concomitant use of moderate CYP3A4 inducers (rifabutin, carbamazepine, phenytoin) must be documented.

#### 9.4.2 Prohibited Therapies

The following medications are prohibited during the study:

- Concurrent anti-cancer medications or therapies, including radiation therapy;
- Any prior or concomitant use of another JAK inhibitor.
- Any investigational medication other than the study drug. Use of such medications within 14 days or 6 half-lives, whichever is longer, prior to the first dose of study drug and during the study through the Follow-up Visit is prohibited.

#### 9.5 Discontinuation of Study Medication(s)

In the event that any subject discontinues the study medication and subsequently the study prior to completion, regardless of reason, reasonable efforts should be made to have the subject return for an early termination visit and have the End-of-treatment procedures completed as described in Section 7.4.

The date the subject discontinued the study medication and the specific reason for discontinuation will be recorded in the eCRF. This will include reasons such as discontinued due to treatment failure or withdrawn due to adverse event. This information will be used to summarize the reasons for study discontinuation and treatment failure.

### 10.0 WITHDRAWAL OF STUDY SUBJECTS

#### 10.1 Withdrawal Criteria and Procedures

##### 10.1.1 Withdrawal of Subjects from Study

**Subjects will be withdrawn from the study for any of the following reasons:**

- In the Investigator's medical judgment, further participation would be injurious to the subject's health or well being
- Positive urine pregnancy test, confirmed by positive serum pregnancy (serum human chorionic gonadotropin) test results

- Consent is withdrawn
- Termination of the study by the Sponsor.
- Termination of the study by the local health authority or IRB/IEC

**If a subject is withdrawn from the study:**

- The study monitor or Sponsor must be notified.
- The reason(s) for withdrawal must be documented in the subject's medical record and eCRF.
- An End-of-treatment visit should be performed.
- All subjects must be followed for safety for at least 30 days after study treatment has ended, or until study drug related toxicities resolve, return to Baseline or are deemed irreversible, whichever is longer.

If a subject is non-compliant in the opinion of the Investigator, the Sponsor-Investigator should be consulted for instruction on handling the subject.

Criteria for discontinuation of study therapy are provided in Section 7.4.

## **10.2 Replacement Subjects**

Non-evaluable subjects will be replaced, at the Sponsor-Investigator's discretion, to assure that a statistically appropriate number of subjects complete the study.

## **10.3 Protocol Deviations**

Subjects must meet eligibility requirements to be enrolled in the study. Major deviations must be reported to the IRB/IEC in accordance with the IRB/IEC requirements. During the course of the study the monitor must notify the Sponsor-Investigator of subjects found not to have met eligibility criteria. The Sponsor-Investigator in collaboration with the Investigator will determine if the subject should be withdrawn from the study.

## **11.0 ADVERSE EVENTS**

### **11.1 Definitions and Reporting**

An Adverse Event for the purposes of this protocol is defined as the appearance of (or worsening of any pre-existing) undesirable sign(s), symptom(s), or medical condition(s) that occur after subject's signed informed consent has been obtained. Abnormal laboratory values or test results occurring after informed consent constitute Adverse Events only if they induce clinical signs or symptoms, are considered clinically significant, require therapy (e.g., hematologic abnormality that requires transfusion), or require changes in study medication(s).

Adverse Events that begin or worsen after informed consent should be recorded in the Adverse Events section of the eCRF. Conditions that were already present at the time of informed consent should be recorded in the Medical History section of the eCRF.

Adverse Event monitoring should be continued for at least 30 days following the last dose of study treatment. Adverse Events (including lab abnormalities that constitute AEs) should be described using a diagnosis whenever possible, rather than individual underlying signs and symptoms. When a clear diagnosis cannot be identified, each sign or symptom should be reported as a separate Adverse Event.

Adverse Events will be assessed according to the Common Terminology Criteria for Adverse Events (CTCAE) version 4.0). If CTCAE grading does not exist for an Adverse Event, the severity of mild, moderate, severe, and life-threatening, or grades 1 - 4, will be used. CTCAE grade 5 (death) will not be used in this study; rather, information about deaths will be collected as an outcome of the event. The occurrence of Adverse Events should be sought by non-directive questioning of the subject during the screening process after signing informed consent and at each visit during the study. Adverse Events also may be detected when they are volunteered by the subject during the screening process or between visits, or through physical examination, laboratory test, or other assessments. As far as possible, each Adverse Event should be evaluated to determine:

- The severity grade (CTCAE grade 1-4)
- Reasonable possibility that AE is related to the study treatment: (no, yes)

- Start and end dates, unless unresolved at final exam
- Action taken with respect to study drug (none, dose adjusted, temporarily interrupted, permanently discontinued, unknown, not applicable)
- Outcome (not recovered/not resolved, recovered/resolved, recovering/resolving, recovered/resolved with sequelae, fatal, unknown)
- Whether it is serious, as per SAE definition provided in Section 11.3.1.

Unlike routine safety assessments, SAEs are monitored continuously and have special reporting requirements, see Section 11.3.2.

All Adverse Events should be treated appropriately. If a concomitant medication or non-drug therapy is given, this action should be recorded on the Adverse Event eCRF.

Once an Adverse Event is detected, it should be followed until its resolution or until it is judged to be permanent, and assessment should be made at each visit (or more frequently, if necessary) of any changes in severity, the suspected relationship to the study drug, the interventions required to treat it, and the outcome.

Disease progression should not be regarded or reported as an Adverse Event itself unless associated with a separate Adverse Event.

Participating sites must agree to comply by UNMC Data and Safety Monitoring Committee (DSMC) procedures. The DSMC will monitor the protocol on at least a quarterly basis and as requested. Sites must also comply with their local IRB requirements. All grade 3 and grade 4 adverse events and all Serious Adverse Events will be reported to the UNMC Eppley Cancer Center Data and Safety Monitoring Committee (DSMC) via the UNMC study coordinator. Sites will be provided with applicable policies and are required to enter all adverse events into the eCRF. Adverse Event information will be collected from the eCRF database and reported to the UNMC DSMC.

## **11.2      Laboratory Test Abnormalities**

### **Definitions and Reporting**

Laboratory abnormalities that constitute an Adverse Event in their own right (are considered clinically significant, induce clinical signs or symptoms, require concomitant therapy or require changes in study treatment), should be recorded on the Adverse Events

eCRF. Whenever possible, a diagnosis, rather than a symptom should be provided (e.g. anemia instead of low hemoglobin). Laboratory abnormalities that meet the criteria for Adverse Events should be followed until they have returned to normal or an adequate explanation of the abnormality is found. When an abnormal laboratory or test result corresponds to a sign/symptom of an already reported Adverse Event, it is not necessary to separately record the lab/test result as an additional event.

Laboratory abnormalities, that do not meet the definition of an Adverse Event, should not be reported as Adverse Events. A grade 3 or 4 event (severe) as per CTCAE does not automatically indicate a SAE unless it meets the definition of serious as defined below and/or as per investigator's discretion. A dose hold or medication for the lab abnormality may be required by the protocol in Section 8.6 and should not contribute to designation of a lab parameter abnormality as a SAE:

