## **5.0 INVESTIGATIONAL PLAN**

### **5.1 Study Endpoints**

- Determination of response rates according to revised Cheson criteria.
- Evaluate safety of oral ruxolitinib in subjects with DLBCL and PTCL according to NCI CTC v. 4.0 criteria.
- Determine progression free survival (PFS), duration of response, and overall survival (OS) in subjects with DLBCL and PTCL
- Explore relationship between responses to oral ruxolitinib (and alterations in GEP signatures as well as biomarker immunophenotypic changes related to JAK2/STAT3, NF-κB, BCR, PI3K/AKT, and mTOR pathways.
- Evaluate potential effect of oral ruxolitinib exposure on JAK2/STAT3 pathway inhibition in serial tumor samples

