**Table 1 Dose Modification Guidelines**

NCI CTCAE Toxicity Grade	Action Required
Thrombocytopenia: Platelets < 35,000 /uL	

• Hold (interrupt dosing)

• Follow CBC at least twice weekly

• If thrombocytopenia resolved to < Grade 2 (50,000/uL, may restart at next lower dose level)

• Subjects in whom benefit is seen and who recover to at least 40,000/uL platelets, may be considered for retreatment with a dose reduction after consultation with the study PI on a case by case basis.

Grade 3 or 4 Neutropenia (ANC <1000/uL)	

• Hold (interrupt dosing)

• Follow CBC at least weekly

• If neutropenia resolves to <math>\leq</math> Grade 2, may restart at next lower dose level

• Use of growth factors is permitted at the discretion of the investigator

• Subjects in whom benefit is seen and who recover to at least grade 3 ANC, may be considered for retreatment with a dose reduction after consultation with the study PI on a case by case basis.

Grade 4 Anemia (life-threatening, urgent intervention indicated)	

• Hold (interrupt dosing)

• Follow CBC at least weekly

• If anemia resolves to <math>\leq</math> Grade 2, may restart at next lower dose level

• Use of transfusions and/or erythropoietin is permitted at the discretion of the investigator

Related Grade 3 non-hematologic Toxicities	

• Hold (interrupt dosing)

• Manage toxicity according to institutional guidelines

• If toxicity resolves to <math>\leq</math> Grade 2 within 2 weeks, the subject may restart at next lower dose level or maintain per the investigator discretion

Related Grade 4 non-hematologic toxicities	

• Discontinue dosing

• Remove subject from the study

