## 12.2.2 Secondary Efficacy Analyses

### Secondary endpoints

#### **Safety endpoint**

All adverse events recorded during the study will be summarized by each subject cohort. The incidence of treatment-emergent adverse events (new or worsening from baseline) will be summarized by severity and type of adverse event. Listings of deaths, SAEs, and AEs leading to early termination of study treatment or premature withdrawal from study will also be provided.

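### The safety analysis counts only recorded adverse events, so whether asymptomatic platelet counts of 35,000 to <50,000/uL appear in it rests on investigator judgement

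*Combined protocol and SAP*

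**What the plan says.** The safety endpoint in 5.1 is "Evaluate safety of oral ruxolitinib in subjects with DLBCL and PTCL according to NCI CTC v. 4.0 criteria".

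Section 11.1 restricts when a laboratory value counts as an AE. Such values "constitute Adverse Events only if they induce clinical signs or symptoms, are considered clinically significant, require therapy", or, as a fourth route, lead to a change in study drug. Section 11.2 repeats the four routes and adds: "Laboratory abnormalities, that do not meet the definition of an Adverse Event, should not be reported as Adverse Events".

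The platelet row of Table 1 (9.2.3) is triggered by "Thrombocytopenia: Platelets < 35,000 /uL". The same row attaches 50,000/uL to Grade 2: "Grade 2 (50,000/uL, may restart at next lower dose level". The neutrophil row starts at "Grade 3 or 4 Neutropenia (ANC <1000/uL", and the anaemia row acts only at Grade 4.

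For the analysis, 12.2.2 says: "The incidence of treatment-emergent adverse events (new or worsening from baseline) will be summarized by severity and type of adverse event". It adds listings of deaths, SAEs and AEs that led to stopping. Adverse Events (12.3.1) is the only subsection of 12.3. No summary of laboratory values by grade and no shift table is planned. Under 11.1 the DSMC monitors at least quarterly and receives grade 3-4 AEs and SAEs, with the AE information drawn from the eCRF database.

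**The concern.** Thrombocytopenia is the toxicity this drug is known for. Sections 3.1 and 3.3 name it as dose-limiting, and 9.2.1 sets the starting dose by platelet count. A reader of the final report will expect the grade 3-4 thrombocytopenia rate to say how often counts fell that low.

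Under the stated rules it may instead say how often counts fell that low and someone judged the fall worth recording. The protocol gives no threshold for clinical significance, so two sites could handle the same count differently. The DSMC would see the same filtered picture, because its feed is built from the same AE entries.

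The blood counts are drawn weekly in cycle 1, on day 1 of every later cycle and at end of treatment (7.1, 8.2.5), but no planned analysis uses them to grade toxicity.

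**Working it through.** **1. Which counts must become AEs.** For an asymptomatic, untreated subject, only two of the four routes in 11.1 remain: a study-drug change, or a judgement of clinical significance. Reading Table 1 against these:

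- Platelets below 35,000/uL: the hold is mandatory, so the value is an AE.
- Platelets 35,000 to <50,000/uL: no hold, reduction or therapy is required. Section 9.2.3 recommends at least weekly counts and 9.2.2 bars escalation, but neither is a therapy or a change of dose. Only the judgement route is certain to be available.
- Neutrophils below 1,000/uL: all grade 3-4 values are held, so there is no gap.
- Anaemia: Table 1 acts only at Grade 4. Transfused anaemia qualifies through the therapy route. What is left is untransfused, untreated grade 3.

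**2. The protocol's background figure.** Section 3.1 reports 40 of 154 myelofibrosis subjects with a grade 3 or 4 platelet decline, made up of 31 grade 3 and 9 grade 4 events. Since 31 + 9 = 40, I treat these as one worst event per subject. Then 40/154 = 25.97%, which matches the stated 26%.

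**3. What an AE-only table would show.** Assume that this rate carries over, and let f be the fraction of grade 3 subjects whose counts stay in the gap and are not reported. The documents do not give f.

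Reported rate = (9 + 31 × (1 − f)) / 154

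| f | Numerator | Reported rate | Expected per 30 | Expected per 90 |
|---|---|---|---|---|
| 0 | 40.00 | 26.0% | 7.8 | 23.4 |
| 0.25 | 32.25 | 20.9% | 6.3 | 18.8 |
| 0.5 | 24.50 | 15.9% | 4.8 | 14.3 |
| 0.6 | 21.40 | 13.9% | 4.2 | 12.5 |

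**4. Where f = 0.6 comes from.** Take grade 3 as 25,000 to <50,000/uL, with lowest counts spread evenly across it. The share above the hold trigger is (50,000 − 35,000) / (50,000 − 25,000) = 0.60. The value f = 0.6 then also needs every one of those counts to go unreported. The 25,000 floor is an assumption: the protocol cites CTCAE v4.0 without printing its limits, and 9.2.3 uses 25,000 only as a monitoring threshold.

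**The case against.** The strongest reply is that the protocol itself treats 50,000/uL as important. A count ever below it rules out escalation (9.2.2), more frequent counts are recommended (9.2.3), and the summary closing 9.2.3 describes the escalation conditions as the absence of significant thrombocytopenia or neutropenia. Section 3.4 allows doses to be lowered for toxicity, so an investigator could reduce the dose above 35,000/uL and open the drug-change route. Section 11.1 also says that AEs may be detected by laboratory test. All of this stands and makes widespread non-reporting less likely. None of it requires an AE entry.

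Four stronger readings are tempting, and the documents do not support them:

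- **Safety is measured only through AEs.** Haematology, chemistry, vital signs and examinations are all scheduled. The shortfall is in what is analysed.
- **The rule bars untreated laboratory abnormalities.** It admits any value judged clinically significant, treated or not. Reporting in the gap is discretionary.
- **Nearly half of grade 3-4 events would be lost.** From step 4, 0.60 × 31 = 18.6 subjects, which is 12% of 154 and 47% of 40. That requires evenly spread lowest counts and no reporting at all in the gap. With half of the gap events reported it falls to 9.3 subjects (6%); with 80% reported, to 3.7 (2%). It is not an upper bound either, since lowest counts clustered near 50,000/uL would raise it.
- **The result is biased against the 26% figure.** No comparison with that figure is planned, and the protocol does not say whether the 40 cases came from laboratory grading or AE reports.

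**Conclusion.** The point holds as a gap in the analysis. Following the reporting rule as written can undercount the named dose-limiting toxicity, to a degree that depends on site judgement, and the planned tables would not reveal it. Error from this source runs one way: the rule can leave out a low count but does not add one. The gap is 35,000 to <50,000/uL for platelets, plus untransfused, untreated grade 3 anaemia.

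The size cannot be fixed from the documents. The range of 20.9% to 13.9% against 26% is illustrative. It rests on the myelofibrosis rate carrying over and on the chosen f. The first assumption is weak: the disease differs, the toxicity is described as dose dependent, and the myelofibrosis study established maximum tolerated doses of 25 mg bid and 100 mg qd, whereas subjects here start at 10 or 15 mg BID. The existence of the gap needs neither assumption, only that 50,000/uL is the lower limit of Grade 2, as Table 1 implies.

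Safety is a descriptive secondary objective. The response endpoint and the futility rules are unaffected.

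**What to change.** In 12.3, add a table for the safety evaluable population, by cohort, of worst post-baseline CTCAE v4.0 grade and shift from baseline for platelets, neutrophils and haemoglobin, derived from the scheduled laboratory values. Include the derived grade 3-4 counts in the quarterly DSMC report. Keep the AE table alongside it, so that readers can see both what was measured and what was judged to be an event. The dose-hold rule in Table 1 stays as it is.

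The cost is a little programming. No new samples or visits are needed, but the sponsor should confirm that the haematology values are entered in the database, because the documents schedule the samples without saying that each value goes into the eCRF. Reported cytopenia rates are likely to be somewhat higher.

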### **11.3      Serious Adverse Events**

#### **11.3.1   Definitions**

Serious Adverse Event (SAE) is defined as one of the following:

- Is fatal or life-threatening (that is, immediate risk of dying)
- Results in persistent or significant disability/incapacity
- Constitutes a congenital anomaly/birth defect
- Is medically significant, i.e., defined as an event that jeopardizes the subject or may require medical or surgical intervention to prevent one of the outcomes listed above. Considered significant by the investigator as an important medical event (s) that may not result in death, be life-threatening, or require hospitalization but may be considered a serious adverse event (s ) when, based upon appropriate medical judgment, they may jeopardize the subject and may require medical or surgical intervention to prevent one of the outcomes listed in this definition.
- Requires inpatient hospitalization or prolongation of existing hospitalization, unless hospitalization is for:

- Routine treatment or monitoring of the studied indication, not associated with any deterioration in condition (specify what this includes)
- Elective or pre-planned treatment for a pre-existing condition that is unrelated to the indication under study and has not worsened since signing the informed consent
- Treatment on an emergency outpatient basis for an event not fulfilling any of the definitions of a SAE given above and not resulting in hospital admission
- Social reasons and respite care in the absence of any deterioration in the subject's general condition
- Any SAEs that are expected due to the condition being treated, including if the SAE is a primary outcome measure, and whether there has been a clear agreement with regulators not to consider these as SAEs, provided the information is collected elsewhere

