### **3.3 Potential Risks and Benefits**

#### Potential Risks

No specific findings in nonclinical repeat dose toxicity studies identify clinical risk other than noting that consequences of immunosuppression may occur. Hypotension and increases in heart rate were noted at a high dose in a cardiovascular preclinical study. However, these findings have not been recapitulated in a clinical setting. The primary clinical risks with ruxolitinib treatment are the potential sequelae of decreased hematopoietic proliferation secondary to the inhibition of growth factor pathways by JAK2 inhibition. Dose-dependent, reversible thrombocytopenia has been observed in the ongoing study in subjects with MF and represents the DLT. Anemia and, less frequently, neutropenia have also been observed in the ongoing study in patients with MF. Increased rates of infection and anemia are potential risks of myelosuppression, and there are multiple sequelae of anemia including the burden and risks of transfusion. A few subjects have had an apparent worsening of their pre-morbid disease symptoms following rapid cessation of ruxolitinib therapy and a gradual tapering and use of steroids in fragile subjects may be considered when stopping ruxolitinib therapy. In healthy volunteers and patients with RA with greater bone marrow reserve, the effects on hematopoietic proliferation appear to be less pronounced.

Pneumonias and herpes zoster infections have been observed in MF patients treated with ruxolitinib. These infections have, in general, ruxolitinib (See Investigator's Brochure) been assessed as unrelated to study medication, and may reflect in large part the

heightened incidence of these infections in this diseased and elderly study population. In ongoing phase 2 and 3 studies, other opportunistic infections have been seen in MF patients, including a serious adverse event of extra-pulmonary tuberculosis.

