### **11.3.2 Reporting**

To ensure subject safety, every SAE, regardless of suspected causality, occurring after the subject has provided informed consent and until at least 30 days after the subject has stopped study treatment must be reported to the Sponsor-Investigator or designee within 24 hours of learning of its occurrence. Any SAEs experienced after this at least 30 day period should only be reported to the Sponsor-Investigator or designee if the investigator suspects a causal relationship to the study drug. Recurrent episodes, complications, or progression of the initial SAE must be reported as follow-up to the original episode within 24 hours of the investigator receiving the follow-up information. An SAE occurring at a different time interval or otherwise considered completely unrelated to a previously reported one should be reported separately as a new event. Serious adverse event collection begins after the subject has signed informed consent and has received study drug. If a subject experiences a SAE after signing informed consent, but prior to receiving ruxolitinib, the event will NOT be collected unless the investigator feels the event may have been caused by a protocol procedure. Previously planned (prior to signing the informed consent document) surgeries should not be reported as SAEs unless the underlying medical condition has worsened during the course of the study.

Information about all SAEs is collected and recorded on the Serious Adverse Event Report Form. The investigator must assess and record the relationship of each SAE to the

study drug, complete the SAE Report Form in English, and send the completed, signed form by fax within 24 hours to the Sponsor-Investigator via a Sponsor-approved method. The investigator must assess if there is a Reasonable possibility that SAE is related to the study treatment: (no, yes)

All serious adverse events regardless of severity or relationship must be reported to the sponsor-investigator within 24 hours of the investigational staff's knowledge. Please send a completed SAE form to:

UNMC, ATTN: [name]		Sentryx
[contact]	AND	[contact]
[contact]		Helpdesk: [name]

The Sponsor-Investigator will follow UNMC IRB and DSMC safety reporting requirements. Participating sites must follow their local IRB and safety reporting requirements.

The original copy of the SAE Report Form and the fax confirmation sheet must be kept with the case report form documentation at the study site.

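### Section 11.3.1 keeps an unedited template exception for disease-expected events, so some hospitalisations could be left out of SAE reporting inconsistently between sites

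*Combined protocol and SAP*

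**What the plan says.** Section 11.3.1 defines an SAE by five criteria: fatal or life-threatening, disabling, congenital anomaly, medically significant, and hospitalised. Only the last carries exceptions: "Requires inpatient hospitalization or prolongation of existing hospitalization, unless hospitalization is for", followed by five items. The fifth begins "Any SAEs that are expected due to the condition being treated, including if the SAE is a primary outcome measure" and continues "whether there has been a clear agreement with regulators not to consider these as SAEs, provided the information is collected elsewhere". The first item, on routine treatment or monitoring, still contains the prompt "specify what this includes".

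Section 11.3.2 requires that "every SAE, regardless of suspected causality" go to the Sponsor-Investigator within 24 hours, up to at least 30 days after treatment. Section 11.1 has the investigator judge seriousness by the definition in 11.3.1. It sends all grade 3 and 4 adverse events and all SAEs to the DSMC, requires every adverse event to be entered in the eCRF, and says that disease progression is not in itself an adverse event. Section 12.2.2 promises listings of SAEs.

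On the drug's risks, section 3.3 states: "Increased rates of infection and anemia are potential risks of myelosuppression". It adds that pneumonia and herpes zoster in myelofibrosis were generally judged unrelated and may in large part reflect how ill and elderly those patients were.

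**The concern.** The fifth exception reads as a note to the protocol's author, not as a rule for a site. It raises the question of a regulator agreement without answering it, and allows for an SAE being the primary outcome when 12.2.1 makes the primary outcome the overall response rate. Left in place, it still sits inside the definition by which each site decides whether an event is serious.

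The exception turns on whether an event is expected from the disease. In this trial that judgement is hard to make and hard to check. Section 3.2 says this is the first study of ruxolitinib in lymphoma, and the synopsis describes an open-label study at four sites with no control group against which to test a disease attribution. If sites apply the exception differently, SAE counts by cohort will partly reflect local reading of the clause. Some hospitalisations that the Sponsor-Investigator should hear of within a day would arrive only as ordinary adverse event data.

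**Working it through.** No figure in the plan depends on this clause, so the check sets the sections side by side.

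1. **Is the clause complete enough to apply?** It needs three things: a list of expected events, a regulator agreement, and a place where the information is otherwise collected. Sections 11.1 to 11.3.2 name none of them.

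2. **What does it act on?** As laid out, only the hospitalisation criterion. The other four criteria have no exception. It concerns events expected from the condition, which here is lymphoma, not events expected from ruxolitinib.

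3. **What happens to an exempted event?** Because 11.1 takes seriousness from 11.3.1, an exempted hospitalisation that meets no other criterion is not an SAE. It loses the 24-hour report, SAE follow-up reports and SUSAR handling (11.3.2), and its line in the SAE listings (12.2.2).

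4. **Does 11.3.2 repair this?** No. The instruction to disregard causality covers events that already meet the definition. There is no formal contradiction, but the two sections pull against each other: reporting is meant to ignore attribution, while the definition brings attribution back in.

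5. **Which events could be affected?** Section 3.3 gives infection and anemia a drug explanation and gives infection a disease explanation, the latter in myelofibrosis. Section 3.1 lists pneumonia, urinary tract infection, anemia and pyrexia among SAEs in the multiple myeloma study. A site could plausibly call such events disease-expected in lymphoma too.

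6. **What still catches them?** A fatal or life-threatening case remains an SAE. So does one judged medically significant: "Is medically significant, i.e., defined as an event that jeopardizes the subject or may require medical or surgical intervention". That route rests on the investigator's judgement, so it does not assure capture of every hospitalised pneumonia. A grade 3 or 4 event also reaches the DSMC, which reviews at least quarterly; 11.1 sets no 24-hour limit for that route.

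7. **Worked case.** Take a patient admitted with a grade 3 pneumonia that is not life-threatening. Site A calls it an SAE, reports it within 24 hours, and it appears in the SAE listing. Site B calls it expected from the lymphoma and enters it in the eCRF as a grade 3 adverse event. The DSMC is told of both, but only the first is expedited and counted as serious. The text of 11.3.1 does not say which site is wrong.

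**The case against.** A reader might infer that the clause takes the drug's own main toxicities out of SAE reporting. The documents do not support that. The wording concerns the condition and not the drug, it is attached to one criterion of five, and severe events have other routes. The related-event counts for anemia and thrombocytopenia in the myelofibrosis study (section 3.1) do not measure the problem either. They are adverse events of any seriousness in another disease, judged related to the drug, and say nothing about hospitalisations lost.

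A second argument is that the exemption is not available at all: with no agreement and no alternative collection named, its own conditions are unmet. That is a fair reading, but not the only one. All adverse events go into the eCRF, so a site could equally regard the information as always collected elsewhere. That both readings are open is the defect.

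Third, the protocol nowhere says that infection or cytopenia is expected from lymphoma. Section 3.4 links limited marrow reserve to prior therapies, and the infection remark in 3.3 is about myelofibrosis and about relatedness, not about withheld reports. This stands as a limit: the overlap is plausible from the protocol's text but not demonstrated for this population.

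Fourth, it might be said that the DSMC loses its fastest signal. That is not shown. The 24-hour report goes to the Sponsor-Investigator, and 11.1 sends SAEs and grade 3 and 4 events to the DSMC through the same coordinator.

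**Conclusion.** The concern holds in a limited form. Section 11.3.1 contains an unfinished exception that lets sites differ on whether some hospitalisations, most plausibly for infection or anemia, are serious. The consequence is loss of expedited reporting and incomplete SAE counts for those events. It is not a loss of all information, and the primary analysis is untouched.

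The size cannot be estimated: the documents give no hospitalisation rate, no SAE rate by attribution, and no indication of how sites would use the clause. The conclusion assumes that the exception belongs under the hospitalisation criterion, as the layout shows, and that some investigators would take it at face value. The item does not fit grammatically after the words that introduce the list. If it were meant to qualify the whole SAE definition its reach would be wider, but it would still concern the disease and not the drug.

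**What to change.** Delete the fifth exception from 11.3.1. The existing statement in 11.1 on disease progression already covers the case for which an exemption is most easily justified, so 11.1, 11.3.1 and 11.3.2 would then agree.

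Deleting the unanswered prompt in the first exception is not part of this fix. It would hide a gap without closing it, because the exception for routine care would stay undefined; the sponsor should supply the missing content.

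The cost is an amendment to one list and a modest number of additional SAE reports. No analysis or sample size changes.
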